11.4.4 Safety Analyses

Unsolicited AEs will be coded by MedDRA for preferred term and system organ class. The proportion of subjects and exact 95% confidence intervals of AEs in aggregate, as well as by MedDRA categories, will be computed. The number of SAEs will be reported by a detailed listing showing the type, MedDRA coding, relevant dates (treatment dosing dates and AE onset and resolution dates), severity, relatedness, and outcome for each event.

11.4.4.1 Analysis of Secondary Safety Outcome Measures

Safety outcome measures will be analyzed in the safety analysis population.

The safety outcome measures are as follows:

1. Incidence of unsolicited non-serious adverse events through 60 days.
2. Incidence of laboratory adverse events (WBC, Hemoglobin, Platelet count, Creatinine, Alkaline Phosphatase, ALT, AST, BUN, and Bilirubin) through 60 days.
3. Incidence of protocol-specified serious adverse events (see section 9.2.3 for details) through 60 days.
4. Incidence of hospitalization through 60 days.

For all safety outcome measures above, the proportion of subjects with events will be presented by treatment arm and overall. Point estimates for proportions and difference in proportions along with the corresponding 95% confidence intervals will be reported. A Barnard's exact test at the 5% two-sided level of significance level will be used for the comparisons of proportions between treatment arms.

11.4.5 Exploratory Analyses

The exploratory outcome measures are as follows:

Clinical Improvement;

1. Time from randomization to initial clinical improvement in Norovirus disease through 28 and 180 days for at least 48 hours, as defined by:

- a. 50% reduction in number of episodes of vomiting and,
 - b. Improvement in PO intake, as judged by the subjects and,
 - c. 50% reduction in the number of episodes of diarrhea as classified by the subject by the Bristol Stool Chart as type 6 or 7 bowel movements and,
2. Time from randomization to initial cessation of vomiting through Day 180 (recurrent vomiting will be considered disease recurrence unless determined to be due to another etiology [i.e. GVHD]).
 3. Time from randomization to subject report of no loss of appetite that is maintained for 48 hours through Day 180 (measure will be first time that the subject reports that they have no “loss of appetite” on their daily diary).
 4. Time from randomization to initial cessation of diarrhea through Day 180 classified by the Bristol Stool Chart as type 6 or 7 bowel movements (recurrent diarrhea will be considered disease recurrence unless determined to be due to another etiology [i.e. GVHD]).
 5. Time from randomization to 50% reduction in the amount of antimotility agents utilized by the subject through Day 180.
 6. Number of days of diarrhea through Days 28 and 180.
 7. Number of stools classified by the Bristol Stool Chart as type 6 or 7 bowel movements through Day 28.
 8. Number of days of IV hydration or total parenteral nutrition (TPN) therapy through Day 28.
 9. Total number of days of hospitalization through Days 28 and 180.
 10. Change in patient-reported quality of life as measured by EuroQOL-5 (global) and IBSQOL (diarrhea specific) [adult] or Euro QOL-5 Peds (global) and PedsQL GI Module [children] from baseline to Day 180.
 11. Change in patient-reported physical function as measured by the NIH PROMIS Physical Function (Adult) Pediatric Global Health (Peds) from baseline to Day 180.
 12. Change in patient-reported emotional distress as measured by the NIH PROMIS Depression, Anxiety, Fatigue (Adult and Peds) from baseline to Day 180.
 13. Change in patient-reported gastrointestinal symptoms as measured by the NIH PROMIS GI (Adult and Peds) symptoms (6 of 8 subscales) from baseline to Day 180.
 14. The effect of co-pathogens, as determined by the BioFire stool pathogen screen, on the primary outcome measure
 15. Time from randomization until initial clinical resolution of Norovirus symptoms for at least 48 hours through Day 180. Clinical resolution will be assessed from the daily diary by the subject and will be defined as cessation of vomiting and no stools classified by the Bristol Stool Chart as diarrhea (Type 6 or 7) from the

total population compared to the subgroup of subjects who do not report chromaturia (discoloration of urine) based on unsolicited self-reporting.

16. Incidence of unsolicited non-serious adverse events (see section 9 for details) through 60 days, laboratory adverse events (WBC, Hemoglobin, Platelet count, Creatinine, Alkaline Phosphatase, ALT, AST, BUN and Bilirubin) through 60 days, protocol-specified serious adverse events (see section 9 for details) through 60 days, and Hospitalization through 60 days from the total population compared to the subgroup of subjects who do not report chromaturia (discoloration of urine) based on unsolicited self-reporting.

Virologic Improvement:

17. Time to ≥ 1 log reduction in stool Norovirus genome copies.
18. Change in quantitative Norovirus load in the stool between Day 1 and Day 7, 14, 21, 28, 60, 120, and 180.
19. Change in Norovirus sequence from Day 1 to Days 28 and 60.
20. The effect of co-pathogens, as determined by the BioFire stool pathogen screen, on the time from the randomization to first negative viral load through 180 days
21. Time from the randomization to first negative viral load through 180 days and the change in viral titer between Day 1 and 180 from the total population compared to the subgroup of subjects who do not report chromaturia (discoloration of urine) based on unsolicited self-reporting.

Immunologic Response:

22. Change in Norovirus-specific serum and stool IgA, IgM and IgG between Day 1 and Day 28 and 60 (stool only).
23. Association between change in total lymphocyte count and T cell subsets at Day 1 and 180 and clinical resolution of symptoms.
24. Association between change in total lymphocyte count and T cell subsets at Day 1 and 180 and undetectable quantitative Norovirus PCR.
25. Association between change in Norovirus-specific serum and stool IgA, IgM and IgG at from Day 1 to Days 28 and 60 (stool only) and clinical resolution of symptoms.
26. Association between change in Norovirus-specific serum and stool IgA, IgM and IgG from Day 1 and Days 28 and 60 (stool only) and undetectable quantitative Norovirus PCR.

Pharmacokinetics and Dose Response:

27. For subjects consenting to PK draws, concentrations of nitazoxanide metabolites (tizoxanide and tizoxanide glucuronide) 1 to 4 hours after the first dose on Day 7 and 10 minutes before the second dose on Day 21.

Natural History of Disease:

28. Time to allograft rejection as per each center team.
29. Time to graft loss as reported to UNOS.
30. Time to death.
31. Time to withdrawal from the study because of intolerance or drug related adverse events.
32. Correlation of secretor status as defined by phenotype and genotype, separately and clinical resolution of Norovirus as defined by the primary endpoint.

Clinical Improvement:

For exploratory outcomes 1 through 5, Kaplan-Meier curves will be produced along with results from a Log-Rank test to compare the time from randomization to clinical improvement in Norovirus disease between the nitazoxanide treated group and the placebo group. The Cox proportional hazards model will be used to estimate the corresponding hazard ratio and 95% confidence interval. If baseline demographic variables are shown to be unbalanced among the treatment groups, those variables will be adjusted in the Cox model.

For exploratory outcomes 6-8, if the number of days of diarrhea follows an approximately normal distribution, then the average number of days will be estimated and compared between the two groups. If the number of days of diarrhea does not follow a normal distribution, a Poisson distribution or non-parametric analysis such as the Wilcoxon test will be considered.

For exploratory outcomes 9, if number of days of hospitalization follows an approximately normal distribution, then the average number of days will be estimated and compared between groups using a two-sample t-test. If the number of days of hospitalization does not follow a normal distribution, a Poisson distribution or a non-parametric analysis such as the Wilcoxon test will be considered.

For exploratory outcomes 10-13, subjects will complete Detailed PRO and Symptom Severity questionnaires at each visit to track changes over time in each of the psychosocial and QOL constructs. An ANCOVA model will be fit using the two groups as the between-subjects factor, time as the within-subjects factor and baseline scores as a covariate. In addition, groups will be compared on unadjusted change over time using a mixed-design analysis of variance (ANOVA) model with all times, including baseline, as a repeated measures factor. Of interest is whether

there are statistically significant pairwise contrasts between the groups on unadjusted change between baseline and subsequent time points, and on adjusted change (controlling for baseline).

For exploratory outcome 14, a Cox proportional hazards model will be utilized to determine the effect of the presence or absence of co-pathogens at any time point on the time to clinical resolution of Norovirus symptoms for at least 48 hours through Day 180. A binary covariate representing the presence or absence of co-pathogens will be included in the model. As an alternative, if it is determined that subjects' co-pathogen status changes often throughout the study, the effect may be considered as a time-varying covariate.

For exploratory outcome 15,16-please see section 11.4.3.3

Virologic Improvement:

For exploratory outcomes 17-19, analysis of Norovirus sequencing data, mutations will be compared between the nitazoxanide and placebo treatment groups. Non-synonymous/synonymous (dN/dS) mutation analysis will be performed for each subject to determine whether selection is occurring within the polymerase, as well as Viral Epidemiology Signature Pattern Analysis (VESPA) and Random Effects Likelihood and Fixed Effects Likelihood (REL and FEL) methods to perform site-specific analyses and to identify trends within the nitazoxanide treatment group and differences between the treatment and placebo groups.

For exploratory outcome 20, a Cox proportional hazards model will be utilized to determine the effect of the presence or absence of co-pathogens at any time point on the time to first negative viral load through 180 days. A binary covariate representing the presence or absence of co-pathogens will be included in the model. As an alternative, if it is determined that subjects' co-pathogen status changes often throughout the study, the effect may be considered as a time-varying covariate.

For exploratory outcome 21, please see section 11.4.3.3

Immunologic Response:

For stool immunoglobulin testing, Day 1 will assess baseline values, Day 28 will assess end of treatment levels and Day 60 will give a single post-treatment level. The proportion of subjects with ≥ 4 -fold rise in Norovirus-specific Ig titers from Day 1 will be assessed at each follow-up time point comparing the nitazoxanide treatment group to the placebo group.

Serum Immunoglobulin Testing (Serum total Ig and Norovirus-specific levels): Day 1 will assess baseline values, Day 28 will assess end of treatment levels. The proportion of subjects with ≥ 4 -fold rise in Norovirus-specific Ig titers from Day 1 will be assessed at Day 28 comparing

the nitazoxanide treatment group to the placebo group. In addition, the ratios of Norovirus-specific IgG to total IgG will also be compared between the nitazoxanide and placebo groups.

For exploratory outcome 22, an ANCOVA model will first be used to compare the treatment and placebo groups with respect to difference in changes of Norovirus-specific serum and stool IgA, IgM and IgG between Day 1 and Day 28 and between Day 1 and Day 60 (for stool only). A mixed effects model will then be used to compare the treatment and placebo groups with respect to difference in the changes of Norovirus-specific serum and stool IgA, IgM and IgG, which will use the longitudinal data observed at all three time points.

For exploratory outcomes 23-26, a Fisher's Z-transformation will be applied to the Pearson correlations between change in total lymphocyte count and T cell subsets at Day 1 and 180 and clinical resolution of symptoms in both the treatment and placebo groups, which will then be compared using a Z-test.

Pharmacokinetics and Dose Response:

For exploratory outcome 27, plasma concentrations of nitazoxanide metabolites in subjects consenting for PK blood draws at two time points will be described and summarized. Descriptive statistics (e.g. n, mean, standard deviation, % CV, median, and range) will be calculated for each sampling time.

Cox proportional hazard regression models will be used to examine the dose response relationship of Day 7 and Day 21 nitazoxanide metabolite concentrations on time from randomization until initial clinical resolution of Norovirus symptoms for at least 48 hours through Day 180. Additional analyses of PK endpoints may be described in the SAP.

Natural History of Disease:

Exploratory outcomes 28-31 are all time-to-event outcomes. They will be analyzed similarly as exploratory outcome 1.

Exploratory outcome 32 will be assessed similarly to exploratory outcome 14.

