solid organ transplant patients with Norovirus.⁽⁴⁹⁾ We retrospectively reviewed data from 67 SOT recipients with diarrhea who tested positive for Norovirus and 67 randomly selected SOT recipients with diarrhea who tested negative for Norovirus. From this data, 35% of all patients evaluated for diarrhea had Norovirus, which was the most common infectious diagnosis among patients with diarrhea; *C. difficile* was the second most common diagnosis in 25% of patients. We found that nearly half of patients with Norovirus were diagnosed without the need for hospitalization. Diarrheal duration was significantly protracted in Norovirus patients with an average of 241 days versus 75 days in the control ($p=0.00065$); 22.4% of Norovirus patients were still having diarrhea at the time of last evaluation suggesting that we are likely underestimating the duration of symptoms. There were 1 patient death and 3 graft failures related to the Norovirus illness within the first year after the onset of diarrhea and 30% of Norovirus patients had a $\geq 20\%$ increase in creatinine within 1 year of the diagnosis. Most (58%) of the Norovirus-infected patients required intravenous hydration on diagnosis and 81% had supra-therapeutic tacrolimus levels at diagnosis.

In another recent study of 116 pediatric solid organ and hematopoietic stem cell transplant recipients with diarrhea, 22% had documented Norovirus infection, making it the most commonly identified enteropathogen.⁽⁵⁰⁾ Over half of these patients had prolonged diarrhea with a median duration of 12.5 days (range 1-324 days) and 29% developed recurrent episode(s) of Norovirus-associated diarrhea. Patients with Norovirus were more likely to require ICU admission (27% vs. 0%, $p = 0.02$), had a greater rise in serum creatinine (median 0.3 vs. 0.2 mg/dL, $p = 0.01$), and experienced greater weight loss (median 1.6 vs. 0.6 kg, $p < 0.01$).

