5.2 Subject Exclusion Criteria

Subjects meeting any of the exclusion criteria at baseline will be excluded from study participation

1. Other identified infectious causes of diarrhea at screening*.
2. Any condition that would, in opinion of the Site Investigator, place the subject at an unacceptable risk of injury or render the subject unable to meet the requirements of the protocol.
3. Subjects receiving oral or intravenous immunoglobulin therapy concurrently or in the 14 days prior to enrollment.
4. Nitazoxanide use for any illness in the previous 30 days prior to randomization.
5. Have received experimental products within 30 days prior to the study entry or plan to receive experimental products at any time during the study
6. Known sensitivity to nitazoxanide or any of the excipients comprising the nitazoxanide tablets.
7. Subjects unable to swallow oral medications.
8. Subjects with ostomy.
9. Women who are pregnant or lactating or have a positive urine pregnancy test at screening/enrollment/Day 1.

Co-enrollment in other studies is allowed if none of the above exclusion criteria are met.

*Alternative diagnosis requiring treatment would be considered a co-infection; if the testing is positive for a pathogen that the PI does not feel is causing the symptoms, they may be included but the PI or his/her designee must document that the positive test is not clinically significant, does not require treatment and is not causing the symptoms making the patient eligible for enrollment.

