Pathogen Screen (BioFire)	Exploratory	1, 180 (all subjects) also 7, 14, 21, 28, 60, 120, and with recurrent diarrhea if unformed stool on study day	1g aliquots	Sites [name] Lab	1g aliquots 1 x 1g required	Frozen	Samples will be shipped to [name] Lab-will provide stool aliquots to [name] Lab ([name]) as requested when ready to perform assay.
Backup Specimen	Exploratory and Future Use	1, 7, 14, 21, 28, 60, 120, 180, and with recurrent diarrhea	1g aliquots	Sites [name] Lab	1g aliquots 3 x 1g required	Frozen	Samples will be shipped to [name] Lab

Initial sample collection tubes, except for the buccal swab, will be labeled with the study number, subject ID number, and date obtained. The buccal swab initial collection tube and all processed sample aliquots to be tested in the central laboratory will be barcoded.

The central laboratory for this study will be [name]'s laboratory at Cincinnati Children's Hospital Medical Center. Northwestern will provide the sites with key required study consumables (e.g. blood and stool collection tubes), shipping containers and FedEx pre-paid shipping labels for all specimens being tested in [name] laboratory

[name] Lab
Attn: [name]
Division of Infectious Diseases, S8.537
[name]
[name]
[name]

In addition, blood collected for the PK testing performed will be stored and sent to SGS Biopharma SA, Wavre, Belgium for testing; samples for PK testing will be sent to SGS Biopharma once per year.

Frozen samples will be batched and shipments to the central laboratory will occur at minimum every other month after communication with [name] study coordinator. All residual specimens will remain in the [name] Laboratory until the end of the study. At this time unused sample aliquots will be returned to the NUCTC laboratory for banking. Detailed instructions for sample preparation, handling, storage and shipment are included in the protocol-specific Manual of Procedures.

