⁶ Diary recorded once a day during the treatment phase and once a day during the longitudinal monitoring phase. Copies of completed pages are collected at each study visit. One pack give an enrollment and additional copies provided at Day 28.

⁷ Stool for pathogen screen will not be performed for formed stool except on Day 1 and 180. An aliquot will be retained for later testing if indicated. Norovirus testing includes quantitative viral load at all time points.

⁸ Sequencing at selected time points.

¹⁰Day 60 pill count only needs to be conducted if the dosing was not completed and medications returned during Study Day 28.

^w Can covert to virtual visit

- § If diarrhea recurs after stopping therapy, would have subject provide a stool specimen for pathogen screen and Norovirus PCR; therapy is at the discretion of the site.
- ¥ The sample must have been produced within 24 hours of the visit and if it exceeds 24 hours it must be disposed. After collection in the stool hat, the subjects can wipe down and disinfect the outside of the container and place it in a bag for transport then refrigerate until they come to their visit with the research staff. Subjects would be encouraged to provide another sample within the visit window and if not, rectal swab may be used for all assays related to stool collection.
- *Vital Signs include weight, Blood Pressure, Respiration, Pulse, Temperature and Height. Height is only measured at Screening/Enrollment/Baseline visit.
- #Derived from Complete Blood Count.
- €Derived from Complete Metabolic Panel.
- ¶Specimen also stored for future use.
- ⓅMust be within 3 days of enrollment. Blood collection includes CBC, Complete Metabolic Panel, T Cell Subsets, and Serum for Ig studies.
- ⁴If Virtual Visit
- ^U If part of PK substudy

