3.3. Study Definitions and Derived Variables

Diarrhea:

Diarrhea will be defined as Type 6 or 7 on the Bristol Stool chart.

Baseline Value:

The baseline value will be defined as the last value obtained prior to the first dose of study product unless otherwise noted.

Additional Nitazoxanide:

Any nitazoxanide reported as a concomitant medication will be considered additional nitazoxanide.

Initial Clinical Resolution of Norovirus Symptoms:

Clinical resolution of Norovirus symptoms will be assessed from the daily diary by the subject and will be defined as:

- Cessation of vomiting and,
- No stools classified by the Bristol Stool Chart as diarrhea (Type 6 or 7).

Subjects will need to have at least two consecutive daily diary entries where they reported no vomiting, no Bristol Stool Type 6, and no Bristol Stool Type 7 to meet the criteria for initial clinical resolution. There are several variables in the daily diary that indicate whether the subject had diarrhea or vomiting for that day.

Daily Diary Diarrhea Questions:

- Phase 1 (Treatment Phase):
 - Number of Bristol Type 6 stools? (Quantitative)
 - Were there too many Bristol Type 6 stools to count? (Qualitative)
 - Number of Bristol Type 7 stools? (Quantitative)
 - Were there too many Bristol Type 7 stools to count? (Qualitative)
- Phase 2 (Longitudinal Phase):
 - Did you have diarrhea today? (By diarrhea, we mean at least ONE bowel movement that could be described as Type 6 or 7.) (Qualitative)

Daily Diary Vomiting Questions:

- Phase 1 (Treatment Phase):
 - Did you have to take another dose because you threw up the first dose within 1 hour? (Qualitative)
 - How many times did you vomit today? (Quantitative)
- Phase 2 (Longitudinal Phase):
 - Did you vomit today? (Qualitative)

For a day to count towards clinical resolution during the treatment phase, the following responses must be recorded in the daily diary entry:

- Both quantitative diarrhea questions must be 0

- Both qualitative diarrhea questions must be missing (i.e. not “yes”)
- The quantitative vomiting questions must be 0
- The qualitative vomiting question must be “no”

For a day to count towards clinical resolution during the longitudinal phase, the following responses must be recorded in the daily diary entry:

- The qualitative diarrhea question must be “no”
- The quantitative vomiting question must be 0

If a daily diary entry is missing, refer to the imputation rules in Section [6.5](#).

Viral Load:

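### Exploratory outcome 14: the default co-pathogen covariate rests on stool screening that depends on the outcome, and the planned tables have no cell for the co-pathogen effect

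*Protocol*

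**What the plan says.** Outcome 14 asks how co-pathogens affect the primary outcome. Protocol 11.4.5 fits a Cox model to "determine the effect of the presence or absence of co-pathogens at any time point on the time to clinical resolution of Norovirus symptoms", with presence or absence as one binary covariate. A time-varying covariate is an optional alternative if "co-pathogen status changes often throughout the study". SAP 8.3 omits the reference to any time point and makes the switch mandatory once that condition is met. It keeps the binary default and does not restrict it to Day 1 or to samples before the event.

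The screening schedule is in Protocol Table 6 (section 8.2.3): "1, 180 (all subjects) also 7, 14, 21, 28, 60, 120, and with recurrent diarrhea if unformed stool on study day". Appendix A, footnote 7, agrees: "Stool for pathogen screen will not be performed for formed stool except on Day 1 and 180". SAP 3.3 and 4.5.1 repeat the rule.

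The event, in SAP 3.3, needs "at least two consecutive daily diary entries where they reported no vomiting, no Bristol Stool Type 6, and no Bristol Stool Type 7".

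The shells for SAP Tables 34-36 define every HR as nitazoxanide to placebo. Their footnotes take the Any Status HR from a stratified Cox model.

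**The concern.** Stool form enters twice. It is part of the event, and from Day 7 to Day 120 it decides whether a subject is tested for the exposure. A subject who stays symptomatic gets more chances of a positive screen than one who resolves early. An ever-positive covariate also accepts the Day 180 screen, or one at recurrence, after the event has happened, so the model conditions on the future. Both features make co-pathogens look as though they delay resolution when they do not.

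The trigger for the time-varying form does not guard against this. It has no threshold, and it concerns how often status changes, not how unequally subjects are tested.

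The outputs have a separate fault. SAP 8.3 promises co-pathogen status as a covariate, but the table footnotes describe a stratified model. A model stratified on co-pathogen status yields no co-pathogen coefficient, and under any reading the printed HR compares treatments. The stated outcome therefore has no cell. The bias could show only as longer medians in the Present rows than in the Absent rows.

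**Working it through.** **1. Event-time model, checked against the plan's own figure.** Inputs from Protocol 11.2: medians 135 days (placebo) and 67.5 days (nitazoxanide), 64 per arm, 90% power. Follow-up is 180 days and times are assumed exponential.
- Probability of resolving by Day 180: placebo 1 − 2^(−180/135) = 0.603; nitazoxanide 1 − 2^(−180/67.5) = 0.843; mean 0.723.
- Events in 128 subjects: 128 × 0.723 = 92.5.
- Power at HR 2: Φ(√(92.5/4) × ln 2 − 1.96) = Φ(1.37) = 91.5%. The plan states 90%, and 91.3% in its table with no re-treatment.
- Attrition: 128/0.80 = 160.

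The model reproduces the plan, so it is used below.

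**2. Unequal testing, by hand.** Assumptions not in the documents: at each of the six conditional visits (Days 7, 14, 21, 28, 60, 120), 70% of unresolved and 30% of resolved subjects give unformed stool (70/30). Detection is 10% per screen and independent between visits.
- Expected screens: resolved before Day 7, 2 + 6 × 0.3 = 3.8; unresolved to Day 180, 2 + 6 × 0.7 = 6.2.
- Probability of being classed as present: 1 − 0.9² × (1 − 0.03)⁶ = 33% against 1 − 0.9² × (1 − 0.07)⁶ = 48%.

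Co-pathogens have no effect here, yet the slow group looks more exposed.

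**3. Effect on the HR, by simulation with no true co-pathogen effect.** Cox model with treatment and ever-positive status, 70/30 testing:

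| Detection per screen | 2% | 5% | 10% | 20% |
|---|---|---|---|---|
| HR, N=160, independent detection | 0.89 | 0.88 | 0.86 | 0.80 |
| False positives at 5% | 4% | 6% | 10% | 21% |
| HR, N=160, status kept between visits with probability 0.5 | 0.95 | 0.94 | 0.93 | 0.92 |
| Median HR, n=31, independent detection | 0.92 | 0.92 | 0.84 | 0.83 |
| False positives, n=31 | 4% | 5% | 6% | 9% |

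Repeat runs differ by about 0.02. If status is kept with probability 0.8, the HR is 0.97-0.98. With stable carriage from Day 1 it is 1.00-1.02. When every visit is screened whatever the stool form, the ever-positive HR is 0.99-1.01, so in this model the unequal testing is the cause.

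**4. Alternatives, N=160, 70/30, detection 5/10/20%.** The time-varying status counts a detection only from its sample date and before the event.
- Stool form among unresolved subjects unrelated to how soon they resolve: time-varying HR 0.98/1.00/0.99.
- Unformed stool less likely in subjects who will resolve sooner (shared normal frailty, log-hazard SD 0.5 or 1.0, logit slope 1): time-varying 0.81-0.90, ever-positive 0.65-0.81, Day 1 status 0.99-1.03.

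**5. Trigger.** Under 70/30 with independent detection, 11/25/44/70% of subjects show any status change at 2/5/10/20% detection. At 2-5% the switch may not be made, although the HR is already 0.88-0.89.

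**6. Outcome 20 (first negative viral load), 10% detection, 70/30.** With correlation 0/0.5/0.8 between clearance and symptom resolution, the ever-positive HR is 1.00/0.94/0.90 and the time-varying HR is 1.00/0.97/0.97. With no correlation there is no bias.

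**The case against.** Several counter-arguments have weight.

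- **The wording about any time point is the protocol's, and the protocol defers detail to the SAP.** This stands as far as it goes: the SAP's fault is an undefined window. An undefined window still permits the ever-positive reading.
- **The size is unknown.** This stands. A reader might infer severe bias: with every unresolved and no resolved subject screened at Days 7-120, N=160 gives HRs of 0.79 down to 0.58 and false-positive rates of 9% up to 70%. Those figures need that extreme contrast and independent redetection at each visit, and the documents support neither. An unresolved subject can hand in a formed stool. A resolved subject can relapse: Protocol 2.1 reports that in one paediatric transplant cohort "29% developed recurrent episode(s) of Norovirus-associated diarrhea".
- **The SAP's time-varying switch already cures the problem.** A reader might infer this from the HRs near 1.00 in the first case of step 4. That result depends on stool form being unrelated to resolution speed among unresolved subjects. If subjects close to resolving pass formed stools sooner, HRs of 0.81-0.90 remain. The switch removes misclassification by later samples and reduces the testing bias, but may not remove it.
- **The bias is smallest where the trigger would fail.** False positives at 2-5% detection are close to nominal, which is one reason for the low grading.
- **Outcome 20 is affected in the same way.** The documents do not support this. Stool form is not part of that endpoint, so bias arises only if viral clearance tracks symptoms.

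**Conclusion.** The concern holds, as a minor point. The documents alone establish that the default covariate is fixed, that no window excludes detections after the event, that screening between Day 7 and Day 120 depends on stool form, and that Tables 34-36 have no cell for the co-pathogen effect. The direction is towards an HR below 1, provided unresolved subjects give unformed stool more often than resolved ones.

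The size cannot be determined. Under 70/30 testing with independent detection it is modest, with HRs of roughly 0.80 to 0.89 at N=160, and close to 1 if carriage persists. Detection and stool-form rates are assumptions throughout.

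No efficacy or safety conclusion rests on this outcome. SAP 14.2 reports 31 subjects enrolled and expects mainly descriptive analyses. The practical risk is that longer Present medians, or an HR below 1 if one is reported, are read as biology.

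**What to change.** In SAP 8.3, and in Protocol 11.4.5 if it can still be amended:

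1. Do not use an ever-positive fixed covariate. Delete the trigger based on frequent status changes.
2. Use Day 1 status, screened in everyone, as the fixed covariate and as the grouping for Present and Absent medians.
3. Report alongside it a time-varying status in which a detection counts only from its sample date and only before the event. State that this may leave some testing bias, for outcome 14 as well as outcome 20.
4. Enter co-pathogen status as a covariate, not a stratum, and add a row to Tables 34-36 with its HR and 95% CI.

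This costs wording, table shells and programming; the samples are already planned. The price is precision. At 2-20% detection, 0.6 to 6.2 of 31 subjects would be positive on Day 1 (31 × 0.02 to 31 × 0.20), and they are selected by the exclusion for "Other identified infectious causes of diarrhea at screening". The chance of five or more Day 1 positives in both arms is about 3% at 20% detection and below 0.1% at 10% or less, so the SAP's five-per-arm rule will probably suppress the Present rows. At n=31 the 95% CI for the time-varying HR typically runs from the estimate divided by 2.5-4.7 to the estimate multiplied by the same factor.

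Screening stored formed stool up to the event would equalise testing. Appendix A allows for it ("An aliquot will be retained for later testing if indicated"), but it adds assay cost and is optional.

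Separately, reconcile the passages on formed Day 180 stool. Protocol 7.1 and 8.2.1 exclude it from screening; Protocol Table 6, Appendix A and SAP 3.3 and 4.5.1 include it.
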